1 PROTOCOL SYNOPSIS

Protocol Synopsis:	
Study Sponsor: NovaSignal Corp. [name] National Institute of Health (NIH)	Protocol No.: NA-01STR-03 Regulatory Class: II Study Device(s): NovaGuide and/or Lucid TCD System Development Phase: Phase 1: Feasibility; Phase 2: Pivotal
Study Title: Evaluate a NeXt Generation Portable Diagnostic Platform for Determination and Immediate Triage of Emergency Large Vessel Stroke (EXPEDITE IIA)	
Overall Study Design: This study is a multi-center, multi-phase, multi-cohort, prospective, randomized, open, blinded endpoint (PROBE), non-significant risk (NSR) device study including up to 420 evaluable subjects measured with the study device(s).	
Objective: The purpose of this study is to collect robust data from the robotic NovaGuide device or the Lucid TCD device to validate the Velocity Curvature Index (VCI) as a diagnostic biomarker tool to drive clinical decision making for assessing cerebral vascular occlusions confirmed by standard of care Computed Tomography Angiography (CTA) imaging.	
Number of Subjects: Phase 1: Up to 216 (54 Cohort A TCD, 54 Cohort A No TCD) (54 Cohort B TCD, 54 Cohort B No TCD) Phase 2: Up to 624 (156 Cohort A TCD, 156 Cohort A No TCD) (156 Cohort B TCD, 156 Cohort B No TCD)	Number of Sites: Phase 1: Up to 3 sites Phase 2: Up to 5 sites
Duration of Study Participation: 
Phase 1 Enrollment: 18 monthsPhase 2 Enrollment: 24 monthsTotal Study Duration: 1 to 7 days	
Phase 1 Study Design	
Phase 1 will include up to 54 subjects enrolled in Cohort A and 54 subjects enrolled in Cohort B. An interim feasibility and safety assessment will be completed after Phase 1.	
Phase 1 and Phase 2 Entry Criteria:	
Cohort A LVO	
Inclusion Criteria	

Subject aged 18 years and olderLarge vessel occlusion of the intracranial ICA, MCA (M1, M2), or multiple areas of the aforementioned locations confirmed by computed tomography angiography (CTA)Subject or Legally Authorized Representative has the ability to provide informed consent and comply with the protocol.	
Exclusion Criteria	

Head CT findings consistent with acute primary intracranial hemorrhage (SAH, ICH, etc.)Hemodynamically unstable patients requiring pharmacological support for hypertension	

Protocol Synopsis:	
Study Sponsor: NovaSignal Corp. [name] National Institute of Health (NIH)	Protocol No.: NA-01STR-03 Regulatory Class: II Study Device(s): NovaGuide and/or Lucid TCD System Development Phase: Phase 1: Feasibility; Phase 2: Pivotal
3. Subjects who underwent partial or full craniotomy 4. Additional intracranial pathologies present (tumor, hydrocephalus, etc.) 5. Anticipated insufficient time to acquire a complete initial TCD scan as described by the protocol 6. Subjects who have a physical limitation preventing placement of the system.	
Cohort B Non-LVO	
Inclusion Criteria	
1. Subject aged 18 years and older 2. Non-large vessel occlusion confirmed by computed tomography angiography (CTA) 3. Subject or Legally Authorized Representative has the ability to provide informed consent and comply with the protocol.	
Exclusion Criteria	
1. CTA findings including: a. Occlusions in the common carotid artery, internal carotid artery, anterior carotid artery, middle cerebral artery (M1 and M2 segments), anterior communicating artery, basilar artery, posterior communicating artery and vertebral arteries. 2. Head CT findings consistent with acute primary intracranial hemorrhage (SAH, ICH, etc.) 3. Hemodynamically unstable patients requiring pharmacological support for hypertension 4. Subjects who underwent partial or full craniotomy 5. Anticipated insufficient time to acquire a complete set of scans as described by the protocol 6. Subjects who have a physical limitation preventing placement of the system.	
Phase 2 Study Design	
Phase 2 will include up to 312 subjects (156 cohort A and 156 in cohort B) presenting with stroke like symptoms for which diagnostic imaging has been ordered. Primary and secondary endpoints will be calculated after completion of Phase 2.	

Protocol Synopsis:	
Study Sponsor: NovaSignal Corp. [name] National Institute of Health (NIH)	Protocol No.: NA-01STR-03
	Regulatory Class: II
	Study Device(s): NovaGuide and/or Lucid TCD System
	Development Phase: Phase 1: Feasibility; Phase 2: Pivotal
Imaging Core Lab Analysis: All imaging data will be sent to a core laboratory which will provide independent quantitative and qualitative assessment of all study data. They will be blinded to the study and radiology report data and provide independent review.	
TCD Data Analysis: All TCD data acquired by the NovaGuide Robotic System or the Lucid M1 System (manual TCD) will be sent to NovaSignal which will provide independent quantitative and qualitative assessment of all study data. They will be blinded to the study and radiology report data and provide independent review.	
Data Analysis: Evaluation of correlation between diagnostic imaging standard of care and VCI biomarker by an independent core laboratory masked to local radiology determination. Success criteria will include clinical validation of VCI biomarker for LVO detection threshold performance at or exceeding 90% ROC-AUC (targeting SEN & SPE greater than 90%) to standard of care imaging.	

Phase 1 & 2 Schedule of Assessments				
Assessments	Cohort A¹ LVO TCD	Cohort B² Non-LVO TCD	Cohort C³ LVO NO TCD	Cohort D³ Non-LVO NO TCD
Informed Consent	X	X	X	X
Medical History	X	X	X	X
NIH Stroke Scale♦	X	X	X	X
Non-Contrast CT♦	X	X	X	X
CT Angiography♦	X	X	X	X
Cohort Assignment	X	X	X	X
Randomization TCD / No TCD	X	X	X	X
TCD Scan (NovaGuide or Lucid)	X	X		
Device-Related Adverse Events	X	X		
Concomitant Medications	X	X		

♦ Standard of Care

1. Cohort A LVO TCD subjects scans will be collected following CTA within a three (3) hour window, prior to treatment (e.g. mechanical thrombectomy).
2. Cohort B Non-LVO TCD subjects scans will be collected within a 24-hour period after enrollment.
3. If randomized to 'No TCD' group in either Cohort, TCD scan will not be conducted, but still followed through to discharge.

1.1 List of Abbreviations

Abbreviation/Term	Definition
AE	Adverse Event
CBF	Cerebral Blood Flow
CBFV	Cerebral Blood Flow Velocity
CFR	Code of Federal Regulations
CE	Conformité Européene
CS	Cerebrospinal
CSF	Cerebrospinal fluid
CT Scan	Computed Axial Tomography Scan
DM	Device Malfunction
DSMB	Data Safety and Monitoring Board
EC	Ethics Committee
eCRF	Electronic Case Report Form
EDC	Electronic Data Capture
EX	Exclusion Criterion
F	Fahrenheit
FDA	Food and Drug Administration
GCP	Good Clinical Practice
HIPAA	Health Insurance Portability and Accountability Act
HOB	Head of Bed
ICF	Informed Consent Form
ICP	Intracranial Pressure
IRB	Institutional Review Board
MCA	Middle Cerebral Artery
SAE	Serious Adverse Event
UADE	Unanticipated Adverse Device Effects
TCD	Transcranial Doppler
TIC	Thermal Index for Cranial Bone

2 BACKGROUND AND RATIONALE OF STUDY

The incidence of Large Vessel Acute Ischemic Stroke (AIS) has been estimated to be approximately 250,000 patients per year in the United States and is the leading cause of disability and fifth leading cause of death. Although endovascular interventions (stentriever) and pharmaceutical (tPA) treatments exist for large vessel occlusion (LVO), their use is limited due to the short time window from symptom onset during which these treatments are indicated to be administered. Moreover, recent estimates suggest only approximately 10% of eligible patients receive interventional treatment which has shown to lead to better outcomes in several world-wide RCTs. Currently, the gold standard for stroke diagnosis is CT angiogram (CTA) which is limited to in-hospital use or a low number of mobile stroke ambulances, all costing multi-millions of dollars, requiring expert operators and IV injection of iodine-rich contrast material. Additionally, the clinical stroke assessment scales (RACE, LAMS, CPSS) used in the field, although low cost and non-invasive, have proven unreliable due to training requirements and low inherent accuracies, with SEN and SPE ranging in a recent study from 0.50-0.64 and 0.83-0.92, respectively[13,14]. In order for intervention to be successful, a standardized, quantitative, field based (prehospital and pre-CTA) diagnostic tool is needed to improve LVO identification and ensure rapid transfer to a capable medical facility.

Goals. Establish clinical viability of a fully automated, non-invasive transcranial Doppler (TCD) derived biomarker based on cerebral hemodynamics for prehospital LVO assessment.

Great strides have been made in AIS treatment over the last decade; however, lack of a quantitative, bedside/field-based diagnostic severely which is suitable for hospital/prehospital use limits access to treatment. We were able to show positive results in a feasibility study (EXPEDITE) of 66 subjects (33 LVOs) for LVO diagnosis in the ER setting using a newly developed TCD-derived digital biomarker termed Velocity Curvature Index (VCI) [15,16]. The VCI biomarker which leverages a machine learning platform which leverages data produced by the NovaGuide System (NovaGuide Robotic System – K180455, NovaSignal Corp., Los Angeles, CA USA). The NovaGuide, a combination of the Lucid M1 System (510k K160442) and the NovaBot accessory, utilized in both phases of the proposed research plan, is capable of TCD signal acquisition in the hospital setting without need of a trained TCD technician for operation or interpretation. Phase I will establish baseline performance characteristics of the hemodynamic biomarker (VCI) and define the study characteristics and context of use for FDA submission. Phase II will provide a comprehensive, multi-site data set for full analytic validation of the biomarker, with the goal of regulatory submission for an expanded indication. The availability of this biomarker will have several potential applications including, monitoring post-intervention patients and supplement triage and transfer protocols for patients suspected of LVOs, which will result in potentially faster and more widespread access to intervention, affording vastly improved outcomes for thousands of potential patients each year. The analogy to the use of EKG for myocardial infarction (MI) which supplements clinical evaluation and more invasive imaging.

TCD ultrasonography is a safe, non-invasive, and reproducible technique that allows the assessment of cerebral blood flow velocity (CBFV) in the large conducting arteries of the head and neck. TCD data collection relies on the level of experience of a TCD technologist to acquire an accurate and high-quality signal from the intracranial vessel(s) of interest, thus per user, the data quality is variable. NovaSignal has developed the NovaGuide System to assist in the TCD data collection such that consistent high-quality data may be obtained independent of the experience of the user.

NovaSignal will collect safety and technical feasibility data regarding the use of TCD ultrasound via the NovaGuide System device in humans. Data collected during this study is for research purposes only. No treatment or healthcare decisions will be made based on study measurements collected in this study.

3 DEVICE DESCRIPTION

3.1 Lucid M1 Transcranial Doppler System

The Lucid M1 System is an adjunctive, portable, non-invasive, non-ionizing radiation, point-of-care TCD diagnostic ultrasound system. It is designed to non-invasively measure and display CBFV over the head and neck with a reusable, non-sterile 2-MHz hand-held probe. It can also be used bilaterally to monitor the blood flow velocity of the vessels insonated via the temporal window of the head with a headset with two reusable, non-sterile 2-MHz monitoring transducers. Additionally, the Lucid M1 System measures the occurrence of transient emboli signals within the blood stream. The Lucid M1 System is an FDA cleared diagnostic medical device, Lucid M1 Transcranial Doppler Ultrasound System, 510k (K160442).

3.2 NovaGuide

The NovaGuide System moves two ultrasound probes around the two temporal regions (Right and Left) of the head to find the transtemporal window and then optimizes CBFV measurements. The system uses TCD data to systematically specify and evaluate probe positions. The NovaGuide System consists of a head-support structure that houses two probe positioning modules, a robotic controller unit and computer tablets. The NovaGuide System is non-invasive and does not deliver energy into a subject. The NovaGuide System is comprised of both The NovaSignal Lucid M1 System and the NovaBot accessory.

For this study, the FDA cleared NovaGuide (K180455) will have study specific modifications that are not FDA cleared.

3.3 Intended use of the device

The NovaSignal Lucid M1 System is a medical ultrasound system intended for use as an adjunct to the standard clinical practices for measuring and displaying cerebral blood flow velocity within the major conducting arteries and veins of the head and neck. Additionally, the Lucid M1 System measures the occurrence of transient emboli signals within the blood stream.

The NovaGuide System when used with the Lucid M1 System is a medical ultrasound device which assists the user in the setup and acquisition of cerebral blood flow velocity via the patient's temporal windows. It is intended for use as an adjunct to standard clinical practices for measuring and displaying cerebral blood flow velocity and the occurrence of transient emboli within the blood stream. The NovaGuide System is intended to be used by persons qualified by training in its safe and effective use.

The NovaGuide System is for use in this study only and is not cleared for use by the FDA. It is labelled with the following statement:

CAUTION: Investigational device. Limited by Federal (or United States) law to investigational use only.

The use of the Lucid M1 System with or without the NovaGuide Robotic System in this study is not for the purposes of diagnosis. This device is being used solely for research to develop technology for assisted TCD signal acquisition. As such, the device is considered a Nonsignificant Risk Device under 21 CFR 812.3(m).

3.4 Contraindications

The Lucid M1 System is not intended to be used in fetal applications or inside a sterile field. Use proposed in this study is consistent with the current FDA cleared and CE Mark approved labelling.

The NovaGuide System is not intended to be used when the following conditions are present:

- The NovaGuide System is not intended to be used in persons younger than 18 years of age.
- The NovaGuide System is not intended to be used in fetal applications.
- The NovaGuide System is not intended to be used inside the sterile field.

3.5 Velocity Curvature Index (VCI)

As part of the feasibility work performed in the initial EXPEDITE study (Expedite a NeXt Generation Portable Diagnostic Platform for Determination and Immediate Triage of Emergency Large Vessel Stroke) between October 2016 and October 2017, advanced forms of CBFV morphology were investigated as potential biomarkers for LVO diagnosis in the ER. Termed Velocity Curvature Index (VCI; or simply “curvature” in the context of cerebral hemodynamics), it provides a quantitative metric which can be used to evaluate a single waveform in isolation, or incorporate information from both cerebral hemispheres. VCI requires only a brief recording of MCA flow to compute. Upon locating the TCD signal associated with flow in the MCA, 15 seconds of the CBFV waveforms are recorded (approximately 15 - 30 TCD “beats”; directly analogous to the EKG heartbeat waveform). The recorded beats are then extracted, smoothed, aligned, and averaged, resulting in a single representative beat waveform for each recording

Having obtained a representative averaged beat waveform, VCI is computed straightforwardly according to the following steps. First, local curvature is computed for each time point. For any time series (including TCD), curvature is a well-defined mathematical property which quantifies the degree to which a curve deviates from being “straight” at a given point. Since curvature is a nonlinear function sensitive to small inflections, we elect to consider only curvature associated with the beat systolic complex, where the signal-to-noise ratio is greatest. The systolic complex (or “beat canopy”) comprises the proportion of the beat with the highest velocities and richest morphological structure.

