4.3 Study Design

This study is a multi-center, multi-Phase, multi-cohort, prospective, randomized, open, blinded endpoint (PROBE), non-significant risk (NSR) device study including up to 420 evaluable subjects measured with the study device(s).

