4.11 Screen Failures

Subject eligibility will be determined by the PI or study team based on their clinical assessment of the potential subject while that patient is undergoing standard of care CTA in the hospital.

For this protocol, a single measurement is defined as a collection of data at a single depth on a single side of the head. A scan is defined as a set of measurements which occur during a single data collection session and can include multiple measurements. A bilateral scan refers to measurements which are collected on each side of the head.

Subjects will be measured with TCD and the de-identified data will be reviewed to determine the quality of the data for analysis. Subjects will be considered screen failures if participant does not meet inclusion and exclusion criteria and if the device is unable to pass the registration process. At any point, the PI or research personnel can end the study.

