4.16.1 NovaGuide System Scanning Technique

The scanning session will consist of an initial set-up and signal search (up to 20 minutes). During this time, the system will search for CBFV signals at depths between 45-65 mm. Once the signal is acquired, the system will monitor the signal for up to 20 minutes or until the PI or research teams end study.

The head cradle of the NovaGuide System is positioned underneath the subject's head and secured to a fixed location (bed, chair, or gurney). The user will affix two registration dots on each side of subject's temples. The subject's head is then positioned into the head cradle. The TCD modules are aligned to the head such that the probes are in contact with the subject's temples (temporal window). The user will register the Headmount to the subject's specific head shape and size. The user will apply gel to improve signal quality. The NovaGuide System will collect data and indicate to the user the scan status. The TCD operator will record the scan up to 20 minutes. Study measurements will not delay nor interfere with the patients' standard of care treatment as the PI or research team can end the study at any point.

Subjects will be evaluated during the scanning period per ALARA ("As Low As Reasonably Achievable") criteria. Scanning may not violate ALARA levels and will be immediately terminated if ALARA criteria reached during a scanning session.

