11 STATISTICAL ANALYSIS

11.1 Phase 1 Statistical Analysis:

Primary Endpoint Analysis: Demonstration of VCI diagnostic performance at or exceeding 85% ROC-AUC (targeting SEN greater than 90%) to standard of care imaging.

Biomarker Validation and Analysis: VCI will be computed for each subject according to the procedure outlined in section 3.5, and group differences will be assessed using appropriate statistical methods. ROC-AUC will be computed detailing separability between groups for comparison to standard of care imaging (CTA) and prehospital/neurological clinical scales, along with SEN, SPE, and accuracy at various levels of diagnostic threshold, including that corresponding to Youden's maximal J-statistic.

Sample size calculation: From the results of our feasibility study, we estimate that expected effect size between VCI distributions for LVO (cohort A) and IHC groups (cohort B) will be large (Cohen's $D > 1.25$), such that only a small number of subjects in each group ($N = 11$) will be sufficient to detect significant differences (alpha of 0.05) with standard statistical power of 80%. However, in Phase 1 we seek to demonstrate the stronger aim of biomarker diagnostic performance in excess of 85% ROC-AUC. Assuming this target AUC is met, then sample size determines the confidence bounds on that estimate. In Phase 1 we require a sample of sufficient size to power confidence in the superiority of VCI diagnostic performance relative to current clinical prehospital stroke assessment scales. As existing preclinical scales top out at 78% AUC, this can be accomplished with a sample of roughly 50 subjects in each patient group, which gives a one-tailed 95% confidence bound on the target 85% AUC of less than 7%. The specification of 54 subjects per group is a target number intended to guarantee acquisition of a sufficient sample assuming at least 90% of target enrollment.

Initial safety endpoint analysis: Throughout the study we will collect adverse events, which will be used to determine the safety of the device within the acute stroke environment. In our EXPEDITE study which is also run in the ER for stroke assessment, the device has been designated minimal risk by the IRB and we have not had any serious adverse events in over 80 subjects. We will continue to closely monitor this metric.

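### Section 11 has no rule for scanned subjects who yield no VCI, so AUC, sensitivity and specificity would describe completed scans only, and the loss can differ between LVO and non-LVO subjects

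*Combined protocol and SAP*

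**What the plan says.** **What VCI needs.** Section 3.5 states: "VCI requires only a brief recording of MCA flow to compute". That recording depends on a successful search for the vessel: "Upon locating the TCD signal associated with flow in the MCA, 15 seconds of the CBFV waveforms are recorded". The same section says VCI can "evaluate a single waveform in isolation, or incorporate information from both cerebral hemispheres". It does not say which form the primary analysis uses.

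**How the scan runs.** Section 4.16.1 allows for "initial set-up and signal search (up to 20 minutes") before monitoring begins. It also lets staff stop whenever they choose: "Study measurements will not delay nor interfere with the patients' standard of care treatment as the PI or research team can end the study at" (the sentence then leaves the moment open).

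**Time available.** Under section 4.16.2, a Cohort A (LVO) scan must be done within 3 hours of CTA and before treatment such as thrombectomy. A Cohort B (non-LVO) scan may be done at any time in the 24 hours after enrolment.

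**Who is counted.** Section 4.3 describes a study "including up to 420 evaluable subjects measured with the study device(s"). *Evaluable* is not defined. Section 4.11 says that, after scanning, "the de-identified data will be reviewed to determine the quality of the data for analysis". It gives no criteria, does not name the reviewer and states no consequence.

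**Analysis.** Section 11.1: "VCI will be computed for each subject according to the procedure outlined in section 3.5". Section 11 names no analysis set. It gives no rule for a scan that finds no signal, stops before the recording is complete or fails the quality review, and it plans no report of how often this happens. The Phase 2 success criterion is an AUC of at least 90%, with sensitivity and specificity above 90% as targets (sections 11.2 and 11.5). Section 11.2 reads the sample size as giving 95% confidence in a population AUC above 87%.

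**The concern.** A subject with no index value cannot be placed on a ROC curve. With no rule to the contrary, anyone who is randomised to TCD and scanned but yields no VCI drops out of all three accuracy measures. The results then describe scans that worked, not scans that were attempted.

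The number lost need not be the same in the two cohorts. LVO scans have a shorter window, and that window closes when treatment starts. This follows from the protocol's own timings and needs no assumption about physiology.

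The stated goal in section 2 is prehospital LVO assessment. For that use, an LVO patient in whom the device returns nothing has not been detected, unless a blank result is itself defined as a positive call. The plan has no such definition.

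**Working it through.** **1. The plan's own precision figure.** The Hanley-McNeil variance of an AUC A with n per group is [A(1−A) + (n−1)(B1−A²) + (n−1)(B2−A²)]/n², where B1 = A/(2−A) and B2 = 2A²/(1+A).

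- Phase 2 (section 11.2: A = 0.90, n = 150): (0.09 + 149×0.00818 + 149×0.04263)/22,500 = 0.000341. The SE is 0.0185, the one-tailed 95% bound is 1.645×0.0185 = 0.0304, and the lower limit is 0.870. This matches the stated 3 points and 87%.
- Phase 1 (section 11.1: A = 0.85, n = 50): the bound is 0.0642, which matches the stated figure of under 7 points.

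Neither calculation has a term for scans without a VCI.

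**2. Precision is not the problem.** If 20% of the 156 per cohort were lost in both cohorts (124 left), the bound would be 0.0334 instead of 0.0298 at 156. Enlarging the sample would not address the issue, which is bias.

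**3. Sensitivity.** Let q be the share of scanned LVO subjects with no VCI. The documents give no value, so 5% to 20% is an assumption. Sensitivity among evaluable LVO subjects is set at 0.90.

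| q | Missing not detected: 0.90(1−q) | Missing read as positive: 0.90(1−q)+q |
|---|---|---|
| 5% | 0.855 | 0.905 |
| 10% | 0.81 | 0.91 |
| 20% | 0.72 | 0.92 |

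Unless a missing VCI is read as positive, the evaluable-only figure exceeds detection per scanned LVO subject by the factor 1/(1−q).

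**4. AUC.** Let fA and fB be the shares without a VCI in the LVO and non-LVO cohorts (also assumed), with an evaluable-only AUC of 0.90. Pairs with both values contribute (1−fA)(1−fB)×0.90. The remaining pairs depend on the scoring rule:

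- worst case (every missing value ranked against the device): (1−fA)(1−fB)×0.90;
- all missing scored negative: add (1−fA)fB + 0.5·fA·fB;
- all missing scored positive: add fA(1−fB) + 0.5·fA·fB;
- best case (every missing value ranked in favour of the device): 1 − (1−fA)(1−fB)×0.10.

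| fA / fB | Worst case | All negative | All positive | Best case |
|---|---|---|---|---|
| 5% / 0% | 0.855 | 0.855 | 0.905 | 0.905 |
| 10% / 0% | 0.810 | 0.810 | 0.910 | 0.910 |
| 20% / 0% | 0.720 | 0.720 | 0.920 | 0.920 |
| 10% / 5% | 0.7695 | 0.817 | 0.867 | 0.9145 |
| 20% / 5% | 0.684 | 0.729 | 0.879 | 0.924 |

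With fB = 0 and missing scored negative, the AUC falls from 0.90 to 0.87 when fA = 1 − 0.87/0.90 = 3.3%. That is about 5 of 156 LVO subjects, and it equals the whole 3-point allowance in section 11.2.

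**5. Direction also depends on who is lost.** Assume an equal-variance binormal model in which the AUC would be 0.90 if every scan gave a VCI. Losing the 10% least abnormal LVO scans raises the evaluable-only AUC to 0.942. Losing the 10% most abnormal lowers it to 0.889.

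**The case against.** The strongest reply is that no sentence in the plan restricts the AUC to evaluable scans. Section 11.1 refers to each subject, and the restriction is inferred from one undefined word in section 4.3 and the quality review in section 4.11. That is correct. But because a missing VCI cannot enter a ROC analysis, silence leads to exclusion by default.

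Several existing features reduce the problem without removing it:

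- Subjects with too little time are excluded at entry in both cohorts (section 4.6). This covers only shortage that is anticipated, not scans that fail after randomisation.
- Section 11.4 blinds the sponsor's TCD assessment to study and radiology data. Section 4.11 does not say that the quality review falls under that blinding.
- Section 4.18 already records scan start and stop times and technical observations, but not the reason why a VCI is missing.

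Scoring every missing VCI as an error can also be called harsh, since a scan stopped for treatment is not a device fault. That is fair, and it is why a best-case counterpart belongs beside the worst case.

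A reader might infer more than the documents support:

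- *Occlusion itself removes the MCA signal.* This is plausible, but no section says so, and section 3.5 allows VCI from a single waveform.
- *Any scan ended early has no VCI.* Section 3.5 needs only about 15 seconds of recording. A scan stopped after that can still give a value.
- *The no-delay claim covers every scan while the accuracy claim does not.* Section 11.1 calculates its guideline metrics in subjects with NovaGuide measurements and does not say whether a no-signal subject is one of them.
- *The planned sample margins (54 against 50, 156 against 150) show the expected loss.* Section 11.1 ties the Phase 1 margin to enrolment shortfall, and section 11.2 gives no reason for the Phase 2 margin. Neither is an unreadable-scan rate.

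**Conclusion.** The point holds as a gap in the definition of the primary analysis. For sensitivity the direction is arithmetic: unless a missing VCI is read as positive, 90% among evaluable LVO subjects is 85.5%, 81% or 72% per scanned LVO subject at 5%, 10% or 20% without a VCI. Those rates are assumed, and the true rate may be small.

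For the AUC, it would be wrong to conclude that the evaluable-only figure is overstated. It may be too high or too low, depending on the loss in each cohort, which subjects are lost and how a missing value is scored. What can be said is that the section 11.2 statement of 95% confidence in a population AUC above 87% applies at most to subjects who yield a VCI. The plan has no analysis that would show whether it extends to all scanned subjects.

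Subjects who fail device registration are a separate matter: section 4.11 treats them as screen failures. This point concerns those who register and are scanned.

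**What to change.** In sections 11.1 and 11.2, before outcome data are examined:

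1. Define *evaluable*, including whether a recording from one side is enough and what the quality criteria are.
2. Add an analysis of AUC, sensitivity and specificity in all subjects randomised to TCD in whom scanning was started. Count a missing VCI as not correctly classified; for the AUC, give it the least favourable rank. Add a best-case counterpart. Report both beside the evaluable-only results. The AUC must be included because it is the success criterion.
3. Report the percentage with a usable VCI by cohort, with the reason: no signal, poor quality, or ended before recording was complete.
4. State in section 4.11 that the quality review is done blind to cohort and CTA result.

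The cost is SAP wording and one reason code on the scan form. The price for the sponsor is that the all-scanned sensitivity and specificity will look less favourable than the evaluable-only figures whenever any scan lacks a VCI.
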